5.1 Background

Type 2 Diabetes mellitus (T2DM) is a chronic, progressive disease characterized by hyperglycemia due to multiple metabolic disorders, including the resistance of peripheral tissues to insulin, inappropriate secretion of insulin, increased glucose production in the liver and hyperglucagonemia [1].

Most part of the patients with T2DM has obesity. Global data indicates that 80% of patients with diabetes mellitus are overweight, and in patients with type 2 diabetes, this proportion is higher. In Russia about 50% of the patients with T2DM are suffering from obesity (body mass index [BMI] > 30 kg/m²) and 45% of patients are overweight (BMI 25-29 kg/m²). In the process of body weight management in patients with T2DM, there are certain problems: unwillingness of the physicians and the patients to modify the lifestyle, the diet and the habits, as well as use of the drug (insulin, sulphonylurea) leading to increase in body weight. Surveys confirm that one third of the physicians do not give to the patients with obesity any recommendations for lifestyle modification in obesity. It indicates that the physicians do not have the tools to long-term change of these parameters [2].

The adipose tissue is the basis for the development of insulin resistance; therefore, obesity is a significant aggravating factor for achievement of the carbohydrate metabolism compensation and is associated with cardiovascular risk factors [3].

The adipose tissue is the potent endocrine organ synthesizing hormones and adipokines, most of which negatively influence on the cardiovascular risk profile (increase in BP, activation of pro-inflammatory and pro-thrombotic processes, atherogenic effects) [4].

According to the one of the largest studies in the diabetes history - Look AHEAD (follow-up for 13.5 years), it was evidenced that in patients with reduced body weight and with the maintenance the result in the course of the study, the parameters of the cardiovascular diseases and mortality, the incidence of the strokes and heart attacks decreased [5].

This study complies with the guidelines for medical care provision for the patients with T2DM in the Russian Federation. The algorithms for specialized medical care of patients with T2DM [6] recommend as the based therapy the combination of the following approaches:

- Diet therapy
- Physical activity
- Antidiabetic drugs
- Education and self-control.

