This study provides the personalized approach to the lifestyle changes in the patients, the development of an optimal exercise and nutrition plan, the change in the behavioral habits of the patient in order to adopt the corrections and to the improve the adaptation, as well as to adjust a drug treatment plan in order to use the agents, indifferent to the body weight.

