5.2 Purpose

This study is aimed to achieve of long-term weight loss in T2DM patients by use of comprehensive lifestyle changes study, providing patients with structured diet, exercise plan,

group behavioral support and group education. Additionally the study is designed to establish that reduction of the body weight leads to the improvement of glycemic and lipid metabolism, and can also reduce blood pressure level. The study is also directed to show that lifestyle changes study in T2DM patients can lead to decreasing of hospitalization rate and healthcare consumption. In order to demonstrate a change from standard of care, data will be collected from a parallel cohort from the same centers.

6 Study objectives

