Hypoglycemia questionnaires	X														X					X
Scale of Borg ⁷		X																		X
HE supply form	X				X				X				X	X	X	X	X	X	X	X

*Acceptable deviation for weekly planned visits (visits 2-13) is +/-1 day from the planned date, monthly visits (visits 14-22) is +/- 3 days from the planned date.

¹ Demographic indicators: age, gender, race.

² Date of diagnosis of diabetes, clinical symptoms.

Therapy for diabetes: insulin (type, dosage), insulin+oral hypoglycemic therapy (type, dosage), sulphonylurea (type, dosage), glinide (type, dosage), metformin (dosage), TZD (dosage), DPP4 (type, dosage), GLP1 (type, dosage), other type of treatment.

Complications of diabetes: cardio-vascular diseases, strokes, retinopathy, neuropathy, nephropathy, diabetic foot, other.

³ Concomitant diseases (cardio-vascular diseases, hypertension, eye diseases, vascular diseases of the brain, gastrointestinal tract diseases, respiratory diseases, liver and bile ducts diseases, kidney diseases, blood diseases, etc.)

⁴ General blood test: hemoglobin, leukocytes (+formula), erythrocytes, thrombocytes, ESR.

⁵ Clinical blood test: crude protein, cholesterol, lipids of low and high density, triglycerides, ALT, AST, KPhK, creatinine, GFR.

⁶ Urine analysis: color, transparency, relative density, traces of protein, sugar in urine, ketone bodies.

⁷ Scale of Borg (scale of individual perception of physical training) is part of Information card (Appendix 8).

Study period and parallel group study design allows achieving of primary end point.

The control group indicators should be coordinated with the indicators of patients in active group. The following should be taken into account when active group is being formed: correspondence of BMI and baseline HbA1c. The decision on whether the patient is included in active or control group is made by the doctor.

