7.6 Risks and benefits

The risk to subjects in this trial will be minimized by compliance with the eligibility criteria and study procedures, close clinical monitoring.

There are no therapy changes or innovations in this study. The drug therapy administration is carried out strictly in accordance with the approved instructions for medical use, only with the registered indications and in accordance with appropriate clinical practice.

The study is designed to establish for patients with T2DM and obesity the reduction of the body weight, improvement of glycemic and lipid metabolism, and reducing blood pressure level. We expect that the study can improve a QoL and reduce diseases complications in the study populations. Nvs survey on hypoglycemia will be used to assess the quality of life in patients (**Appendix 2**).

8 Population

The study is expected to include approximately 100 patients with T2DM and obesity. It is planned to have 100 patients in the active group who will be on active life style management; the control group will be 30 patients who will be matched with active group in terms of their indicators. Both groups will receive standard drug therapy for diabetes.

The control group should match the active group. The following criteria should be taken into account (criteria of inclusion and exclusion): match in BMI (<30; ≥30) and baseline HbA1c (<7.5; ≥7.5). The decision to include a patient into active or control group should be made by a doctor.

Drop-out of patients is expected for about 20% of patients compared with the originally included population. The drop-out criteria is three in a row missed group classes in the first 12 weeks of the study in active group.

The drop-out in control group is not expected.

Patients will be distributed among two participating research centers.

The study will be executed in two sites, the [REDACTED] in Moscow and the [REDACTED] in Kazan. The adult patients with T2DM (men and women at the age of more than 18 years) will be under the observation if they need in the active weight loss according to the physician's decision and if a doctor decides that the active approach is necessary.

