12.1 Treatment response variables

Descriptive statistics for body weight (kg), body mass index (kg/m²), waist circumference (WC, cm) and waist to hip ratio (WHR), HbA1c%, fasting blood glucose (mmol/L), lipid profile (cholesterol, triglycerides, LDL, HDL) values together with absolute and relative (%) changes from baseline, as well as systolic and diastolic blood pressure (mmHg) values together with absolute changes, will be tabulated by visit for the FAS population. In addition, descriptive statistics for the above variables and their changes will be tabulated for visits corresponding to Weeks 12, 24, 36, 48, after the imputation of missing values using LOCF approach.

The primary endpoint - the number (proportion) of patients for whom body weight decreased by at least 5% compared to baseline values at 12 months of observation - will be analyzed in FAS (LOCF), additionally the primary endpoint analysis will be repeated in the Per Protocol Set (PP).

The number and proportion of patients with a decrease in body weight of at least 5% compared to the baseline values at 12 months of observation will be tabulated based on available measurements and based on imputed (LOCF) values in the FAS population. The results for the primary endpoint will also be presented by centers.

To compare proportions between groups, the main analysis of the primary endpoint will be carried out using logistic regression with the calculation of the odds ratio with 95% CI. In order to adjust for the potential confounding factors, potentially influencing factors such as age, gender, baseline value of the body mass index, the duration of the disease, baseline level of HbA1c will be included in the regression model.

As part of the sensitivity analysis, the primary endpoint will be analyzed without imputation of missing values using the GEE (Generalized Estimating Equations) method, taking into account the correlation of the repeated measurements at different visits for each patient.

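### The doctor chooses the group, but the primary model and its checks do not prespecify baseline insulin or sulphonylurea use, which the protocol itself links to weight gain

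*SAP*

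**What the plan says.** **Allocation.** The study is not randomised. The protocol's design text states: "The decision on whether the patient is included in active or control group is made by the doctor". Protocol section 8 limits the matching of controls to "match in BMI (<30; ≥30) and baseline HbA1c (<7.5; ≥7.5", and SAP section 6 repeats both points.

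**Adjustment.** For the primary logistic model, SAP 12.1 states that "factors such as age, gender, baseline value of the body mass index, the duration of the disease, baseline level of HbA1c will be included". Protocol section 13 names the same five factors as a closed list; the SAP introduces them with *such as*. The per-protocol analysis repeats the primary analysis. The GEE sensitivity analysis draws on the same five factors and keeps each only if p<0.1.

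**The drugs.** Among the obstacles to weight control, Protocol 5.1 lists "use of the drug (insulin, sulphonylurea) leading to increase in body weight". The diabetes-history footnote to the visit table records "Therapy for diabetes: insulin (type, dosage), insulin+oral hypoglycemic therapy (type, dosage), sulphonylurea (type, dosage" and so on for other classes, and Protocol section 9 requires diabetes drugs in use at entry to be entered in the eCRF. SAP section 11 plans frequency tables of glucose-lowering therapy during the study (Table 2.3), with a patient listing (Listing 3.1). Drug class is not among the baseline characteristics in SAP section 10 and is named in no model.

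**The concern.** When a clinician chooses the group, a variable that affects both that choice and the outcome biases the comparison unless it is adjusted for. The protocol says that insulin and sulphonylurea affect weight. It also gives reasons why the doctor might take them into account. The diet framework in Protocol section 10 is headed for patients not on insulin. The exercise text warns of hypoglycaemia with insulin and agents that stimulate insulin secretion. Patients on these drugs are nevertheless eligible. In the other direction, patients enter the programme, in the words of Protocol section 8, "will be under the observation if they need in the active weight loss", which could favour those on drugs that raise weight.

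At stake is the primary odds ratio. The per-protocol and GEE analyses use the same covariates or fewer, so neither would reveal this confounding.

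**Working it through.** **The plan's own figure.** The documents give no figure for this bias. The only related number is the sample size (100 and 30, 20% dropout, 80% power, 5% mean difference), and no SD is stated. The figure is consistent with a two-sided test if SD = 5 / [2.80 × √(1/80 + 1/30)] ≈ 8.3 points. The present point does not depend on it.

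**Inputs.** The documents give no drug use by group and no drug effect on response, so all of these are assumptions:
- response among patients not on these drugs, p0: 5-20%;
- odds of response in users relative to non-users, k: 0.7-0.8 (mild) or 0.33-0.5 (strong);
- gap in use between groups: 10, 20 or 40 percentage points around 40%.

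**Closed form, true programme odds ratio 1.** User response p1 has odds k × p0/(1−p0). Each group's rate is use × p1 + (1−use) × p0, and the apparent odds ratio follows.
- Mild example: p0 = 0.20, k = 0.7, use 30% active and 50% control. User odds 0.25 × 0.7 = 0.175, so p1 = 0.149. Active 0.3 × 0.149 + 0.7 × 0.20 = 0.185; control 0.5 × 0.149 + 0.5 × 0.20 = 0.174; odds ratio 1.07.
- Strong example: p0 = 0.20, k = 0.33, use 20% and 60%. p1 = 0.076; active 0.175, control 0.126; odds ratio 1.48.

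Ranges over p0 of 5-20%, with the reverse (active group uses more) in brackets:

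| Use, active/control | Mild, k 0.7-0.8 | Strong, k 0.33-0.5 |
|---|---|---|
| 35/45% | 1.022-1.035 (0.966-0.978) | 1.065-1.102 (0.908-0.939) |
| 30/50% | 1.045-1.072 (0.933-0.957) | 1.135-1.214 (0.824-0.881) |
| 20/60% | 1.091-1.149 (0.870-0.916) | 1.288-1.478 (0.677-0.776) |

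With balanced use the odds ratio is 1.00.

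**How much the planned covariates absorb.** HbA1c and disease duration may partly stand in for drug use. A large simulated population (each correlated 0.3-0.5 with drug propensity, p0 15%, 20-40-point gaps, k 0.33-0.8) was fitted with both in the model. If they share the imbalance, 1.02-1.40 (or 0.73-0.98) remains. Adding the drug indicator gives 1.00.

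**Could chance alone produce the gap?** At 40% use, SE = √[0.4 × 0.6 × (1/100 + 1/30)] = 0.102, so a gap of 20 points or more in either direction has probability about 0.05. A larger gap would point to selection.

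**Trial-sized simulations (100 and 30).**
- True odds ratio 1, p0 30-40%, k 0.33-0.5, use 30/70%: the five-covariate model gives a median of 1.30-1.60 and two-sided error of about 6-12%. Adding the drug term alone gives about 0.99-1.05 and about 4-5%.
- One-sided false positives at about 17-20% response were 1.9-2.4% with a 20-point gap, not above the nominal 2.5%. They were 3.1-4.8% with a 40-point gap, and up to 7.5% in another set of runs.
- The plan's effect, with an assumed SD of 6, gives response 50% active and 1 − Φ(5/6) = 20% control, an odds ratio of about 4. With k 0.33 and use 60/20%, the five-covariate model gives a median of 2.65 and power 49%. With drug and centre indicators added, these are 4.38 and 78%. With the gap reversed, 5.97 becomes 4.42. With balanced use, power is 80% without and 83% with the two terms.

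**The case against.** The strongest reply is about size. Every input is assumed. With a mild drug effect the shift is at most ln 1.15 = 0.14 on the log scale, against simulated standard errors of 0.52-0.81, so about a quarter of one standard error or less. That stands, and it limits the claim.

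The cues to selection are also soft. The diet and exercise passages restate national guidance and are not allocation rules, and the need for weight loss points the other way. A reader might infer that allocation did depend on these drugs, or that the result will favour the programme. The documents support neither.

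A reader might also infer that the plan ignores drug therapy or forbids the covariate. It does neither. Table 2.3 and Listing 3.1 would probably show a substantial imbalance, and *such as* leaves room for the term. But a table does not adjust, and an open list lets the choice be made after the data are seen in an open-label study.

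Extending the point to centre is tempting too. There is little basis for it: "data will be collected from a parallel cohort from the same centers", and SAP 12.1 already presents primary results by centre. With the same centre mix in both groups there is no bias.

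One limit on the remedy stands. The programme may "adjust a drug treatment plan in order to use the agents, indifferent to the body weight", so baseline use could act differently in the two groups. A main effect adjusts only for a common effect.

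**Conclusion.** The concern holds in this form: the primary model, its per-protocol repeat and the GEE check do not prespecify a recorded baseline variable that the protocol itself ties to weight, in a study where the doctor chooses the group. If use is unbalanced, the three analyses share the bias.

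Direction and size are unknown from the documents. On the assumptions above, gaps of 10-20 points with a mild drug effect move a true odds ratio of 1 to only 1.02-1.07 (or 0.93-0.98), and even a 40-point gap gives no more than 1.15 (or 0.87). The bias becomes material, up to about 1.5 or down to 0.68, only when a large gap meets a strong effect. It would be wrong to infer that the trial's conclusion is likely to reverse. The change is worth making because the remedy is cheap and the confounder comes from the sponsor's own text.

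**What to change.** In SAP 12.1, prespecify one yes/no indicator of insulin and/or sulphonylurea use at entry. Enter it as a main effect in the primary logistic model, its per-protocol repeat and the GEE check of the weight-responder endpoint, and exempt it from the p<0.1 selection. Use baseline rather than on-study therapy, because drugs may be changed within the programme or as weight falls (Protocol 5.1; SAP section 2). Tabulate baseline use by group.

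A centre indicator is optional and of low priority. This rationale does not require the drug term in the HbA1c, blood pressure or lipid models. The wording should not bar other prespecified confounders: inability to exercise, for example, excludes patients from the active group only.

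**Cost.** SAP wording and one term from data already recorded; no change of estimator or software. The standard error of the group log odds ratio rises by about 1-13%, depending on imbalance. Model terms go from six (group plus five covariates) to seven:
- plan's scenario, 100 × 0.50 + 30 × 0.20 = 56 events: 9.3 to 8.0 events per term;
- 20% response in both groups, 26 events: 4.3 to 3.7;
- 10% response, 13 events: 2.2 to 1.9.

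The last case is thin with or without the extra term. The per-protocol set, being smaller, will have fewer events still.

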12.3 Database management and quality control

Novartis staff, or CRO working on behalf of Novartis, review the data entered into the eCRF by investigational staff for completeness and accuracy and instruct the site personnel to make any required corrections or additions.

Queries are sent to the investigational site using an electronic data query. Designated investigator site staff is required to respond to the query and confirm or correct the data.

Concomitant medications entered into the database will be coded using the World Health Organization (WHO) Drug Reference List, which employs the Anatomical Therapeutic Chemical classification system.

Medical history and AEs will be coded using the Medical Dictionary for Regulatory Activities (MedDRA) terminology.

13 Data analysis

Descriptive statistics will be applied in the study to describe the sample size of the patients at baseline and at follow-up visits, demographic data recorded during the examination of the study parameters, as well as their changes.

The choice of parametric or non-parametric criteria for testing statistical hypotheses will be determined on the basis of the Kolmogorov-Smirnov criteria (conclusion of the presence or absence of statistically significant differences between the distribution of the respective parameter and the normal one), as well as with the graphical methods.

AE data will be presented as an absolute number and as the proportion of the patients with any AE, according to the organ systems and specific AE with corresponding 95% confidence intervals (CI). The association between therapy duration and AE (SAE) risk will be analyzed on the basis of the proportional-hazards regression model of the survival analysis. Age, sex, BMI, disease duration, baseline HbA1c, will be taken into account in the model for the control of potential confounding factors. Secondary indicators will be analyzed the same way.

The primary analysis of the proportion of the patients with response on the treatment will be performed using multivariate logistic regression and calculating odds ratios with

corresponding 95% CI. To control the potential confounding factors, age, sex, BMI, disease duration, the baseline values of HbA1c will be taken into account in the regression model.

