6.2 Exclusion criteria

Patients fulfilling any of the following criteria are not eligible for inclusion in this study:

1. Pregnant or nursing (lactating) women, where pregnancy is defined as the state of a female after conception and until the termination of gestation.
2. Type 1 diabetes
3. Proliferative retinopathy, hemorrhage and disinsertion of retina
4. Renal impairment: serum creatinine >1.5 mg/dL, creatinine clearance < 40 ml/min and/or proteinuria.
5. The lack of ability to perform the physical exercises due to the orthopedic or cardiovascular disorders *
6. Chronic alcoholism, acute alcoholic intoxication

* - the criterion is applicable only for the active group.

7 Population determination for statistical analysis

- All enrolled patients: all patients who signed informed consent for inclusion in the study. The population will be used for the disposition data summaries and listings.
- Safety Population: all patients of the active group included in the study, who started participating in the lifestyle correction program, and all patients of the

control group for whom the observation was started. The population will be used to summarize adverse events and other safety parameters.

- Full Analysis Set (FAS): all patients who provided baseline data and data to evaluate at least one efficacy parameter after the onset of observation. The population will be used for efficacy analyses.
- Per Protocol Set (PP): all FAS patients who did not have any major protocol deviations. The population was used to analyze the primary endpoint (sensitivity analysis).

The patient can be excluded from the Per Protocol Set for the following reasons:

- did not attend more than 3 consecutive classes in the active group;
- missed at least 50% classes of the program;
- did not provide data for the estimation of the primary endpoint.

8 General considerations

The latest available estimates before the start of the program for the active group and data from the Visit 1 for the control group will be used as the baseline values for the analysis of quantitative efficacy and safety parameters. The baseline visit is Visit 2 (Week 1) for the active group and Visit 1 for the control group.

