The model will include group, time (visit) and group*time interaction. In addition to group, time and interaction term, only significant influencing factors (age, gender, baseline body mass index, disease duration, baseline HbA1c) ($p < 0.1$) will be included in the model. A first order autoregressive covariance structure [AR (1)] will be used in the model. If convergence is not achieved, other covariance structures (Independent, unstructured covariance structure (Unstructured)) will be tested as possible alternatives. Differences between groups (active group - control group) will be assessed using interaction term group*time, calculating the adjusted means and corresponding 95% confidence intervals for the group*time interaction.

Secondary dichotomous variables - a decrease in body weight by at least 5% at 3, 6, 9 months of observation and at least 10% of the baseline values at 3, 6, 9, 12 months of observation will be analyzed in a similar manner.

Secondary dichotomous endpoints – a decrease of HbA1c level by at least 0.5% from baseline, achievement of HbA1c $\leq 7\%$ by 12 months of observation, a decrease in SBP and DBP by at least 5 mmHg at 3, 6, 9, 12 months of observation - will be analyzed using GEE with the imputation of missing values.

After the imputation of missing values, the endpoints representing the absolute and relative (%) changes in the quantitative variables for 3, 6, 9 and 12 months will be analyzed using the GEE method. The initial values of the relevant variable, age, sex, baseline body mass index, duration of the disease, and the initial value of HbA1c% will be used as factors and covariates. 95% confidence intervals for mean values of the parameters in both groups will be presented, as well as for the difference in the mean values between the compared groups adjusted for the influence of these factors.

In case of significant deviations from the normal distribution (verified using graphical methods), the logarithmic transformation or nonparametric Mann-Whitney U-test will be used as possible alternatives.

All data on primary and secondary endpoints will also be presented in the form of listings.

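### The no-imputation GEE sensitivity analysis of the primary endpoint keeps the five confounders only if p<0.1, whereas the main model includes all five; the effect is modest and the fix is wording only

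*SAP*

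**What the plan says.** **Main analysis.** SAP 12.1 plans a logistic regression on the FAS with LOCF. It lists age, gender, baseline BMI and two more: "the duration of the disease, baseline level of HbA1c will be included in the regression model". Protocol Section 13 names the same five for the primary regression, ending "the baseline values of HbA1c will be taken into account in the regression model". Neither text applies a significance test.

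**Sensitivity analysis.** In SAP 12.1 "the primary endpoint will be analyzed without imputation of missing values using the GEE" method, with group, visit and their interaction and an AR(1) structure (Table 4.1.3.3). Beyond those terms it keeps "only significant influencing factors (age, gender, baseline body mass index, disease duration, baseline HbA1c") at p<0.1. The output is obtained by "calculating the adjusted means and corresponding 95% confidence intervals for the group*time interaction".

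**Other checks on missing data.** Responder counts "will be tabulated based on available measurements and based on imputed (LOCF) values in the FAS population", without adjustment. The primary analysis is also repeated in the PP set. Under SAP Section 7 a patient can leave that set because he or she "did not provide data for the estimation of the primary endpoint", but also because of poor class attendance.

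**Quantitative secondary endpoints.** The GEE adjusts for the baseline value of the variable, age, sex, baseline BMI and disease duration, and "the initial value of HbA1c% will be used as factors and covariates". If graphs show marked non-normality, a log transformation or a Mann-Whitney test may be used instead.

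**Allocation.** The physician decides the group (SAP Section 6, Protocol Section 8). Control formation considers only BMI and HbA1c bands.

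**The concern.** The five factors are in the main model because the groups are not randomised. Whether a factor reaches p<0.1 in about 130 patients says little about whether it confounds: a factor can be imbalanced and prognostic and still miss the threshold. Age, sex and disease duration are not considered when controls are formed, so imbalance in them is plausible.

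The GEE is the only modelled analysis of the primary endpoint on the full FAS without LOCF. Drop-out of 20% is expected, with none assumed in control, so readers will look to this analysis. If its covariates change together with its missing-data handling, a difference from the main result has one more possible cause. The SAP also leaves open whether p comes from a joint, one-at-a-time or stepwise fit, so two analysts could report different models.

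The Mann-Whitney fallback raises a related issue. It takes no covariates, so it cannot deliver the adjusted between-group difference and CI that SAP 12.1 promises.

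**Working it through.** The documents give no figure for this point: no expected imbalance, covariate effect or responder rate. Only the group sizes (100 v 30) and drop-out (20% active, none in control) come from them. The rest is assumed and shown as ranges.

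**1. The rules side by side**

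| Analysis | Missing data | Covariates |
|---|---|---|
| Main logistic, FAS | LOCF | all five |
| GEE sensitivity, FAS | none imputed | those of the five with p<0.1 |
| GEE, quantitative endpoints | imputed | baseline value and all five |
| Mann-Whitney fallback | not stated | none |

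SAP Section 16 (changes to the plan) gives no reason for the screen.

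**2. How often is a real confounder dropped?** Take one visit, 80 + 30 = 110 patients and a response rate of 1/(1+e^0.7) = 0.332. The SE of a log OR per SD is about 1/√(110 × 0.332 × 0.668) = 0.2025.
- OR 1.3 per SD: z = 0.262/0.2025 = 1.30. P(kept) ≈ P(Z > 1.645 − 1.30) ≈ 0.36, so it is dropped in about 64%.
- OR 1.5 per SD: z = 0.405/0.2025 = 2.00. It is dropped in about 36%.

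Single-visit simulation gave 64-65% and 38-42%. A full GEE simulation gave 42-63% for at least one real confounder.

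**3. Why the odds ratio moves little.** Dropping a covariate shifts the group log OR by roughly its estimated coefficient times its imbalance. A dropped factor has an estimated coefficient below 1.645 × 0.2025 = 0.333. At an imbalance of 0.4 SD the shift is therefore at most about 0.333 × 0.4 = 0.133, or e^0.133 = 1.14 (14%) per factor.

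**4. GEE simulation.** There were 1,500 datasets per setting, 100 v 30, visits at weeks 12, 24, 36 and 48, AR(1), robust SE, and 20% active drop-out at random. BMI and HbA1c were balanced. Confounding was A: one factor, 0.4 SD, OR 1.3; B: two factors, 0.4 SD, OR 1.4; C: three factors, 0.5 SD, OR 1.3-1.5. The table shows month-12 rejection (%) as all five / joint screen / one-at-a-time screen.

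| Setting | No effect (30% responders) | 50% v 20% responders |
|---|---|---|
| A | 3.7 / 3.9 / 3.9 | 81.8 / 83.1 / 83.0 |
| B | 4.4 / 4.8 / 4.7 | 78.4 / 80.5 / 81.6 |
| C | 5.3 / 5.9 / 5.9 | 70.4 / 73.2 / 74.9 |

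The screen moved the month-12 OR by a median of 4-7% (0.06-0.13 SE), and by at least 12-27% in one trial in ten. The p<0.05 conclusion changed in 1-3% of null trials and in 2.5-5.4% at 50% v 20%. In C the mean log OR was 1.472 with all five and 1.511 or 1.530 screened, an excess of 0.039-0.058, or 4-6% on the OR. Part of the apparent power gain is therefore confounding left in. A separate single-visit check gave a median shift of 7-15%, with null rejection of 5-7% screened v 4-6% with all five.

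**5. What the fix leaves.** With the same five covariates, GEE still differs from the LOCF logistic OR by a median of 7-11%, against 8-13% with screening.

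**6. Mann-Whitney on change.** Let the groups differ at baseline by d SD, with baseline/follow-up correlation ρ and unit SDs. √(1/100 + 1/30) = 0.208. Two meanings of no effect are possible; take d = 0.5.
- *Equal at follow-up given baseline.* Mean change differs by (1−ρ)d; the SD of change is √(2(1−ρ)). For ρ = 0.5, z = 0.25/0.208 = 1.20; for ρ = 0.7, z = 0.15/(0.775 × 0.208) = 0.93. Expected rejection is about 22% and 15%. Simulation gave 14-23% for Mann-Whitney and about 5% for the adjusted model.
- *Stable pre-existing difference.* Change does not differ, but the baseline-adjusted difference is (1−ρ)d with residual SD √(1−ρ²). For ρ = 0.5, z = 0.25/(0.866 × 0.208) = 1.39; for ρ = 0.7, z = 0.15/(0.714 × 0.208) = 1.01. Expected rejection is about 28% and 17%. Simulation gave 16-27% for the adjusted model and 4-5% for Mann-Whitney.

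**The case against.** The strongest reply is that the screening hardly matters. It touches one supportive table, type I error moves by 0.2-0.6 points within a setting, and model form and missing-data assumptions drive most of the gap to LOCF. All of that stands and limits the point to a modest one. The 42-63% drop rate sounds alarming, but it comes from weak assumed effects that barely move the estimate. What remains is that the rule is undefined, at odds with the rest of the plan, and free to remove.

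On the fallback, the reply is that it is optional, that a log transformation can keep the covariates, and that Protocol Section 13 itself allows non-parametric methods. This also stands, so deleting Mann-Whitney outright would depart from the protocol.

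Three stronger readings are tempting, and the documents do not support them:
- *Mann-Whitney inflates false positives to 15-23%.* That holds only if the groups would be equal given baseline, and only at a 0.5 SD imbalance. Under a stable difference the baseline-adjusted model is the one that over-rejects. The documents do not say which applies.
- *The screen reaches the weight-responder secondary endpoints.* SAP 12.1 says that they are handled similarly to the primary. But Section 16 does not list them as moved to GEE, and only Table 4.1.3.3 is titled as a GEE table.
- *The primary result is at risk.* The main and PP analyses use no screen.

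**Conclusion.** The point holds as an optional improvement. Screening at p<0.1 can remove a real confounder from the one modelled full-FAS analysis of the primary endpoint without LOCF, and it adds an avoidable difference from the main model. Under assumed confounding the median OR shift is roughly 4-15%, with little change in type I error. In the single-visit simulations the largest null rejection was 7.2% screened v 5.1% with all five, at an assumed imbalance of 0.8 SD and OR 1.5 per SD. These sizes rest on assumed imbalances and effects and are not estimates for this trial.

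The secondary point holds in a narrow form: the Mann-Whitney option drops the promised baseline-value and five-factor adjustment, changes what is estimated, and has no rule for when it is chosen over the log transformation. No error rate can be attached to it.

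**What to change.** - **GEE sensitivity model (SAP 12.1).** Include age, gender, baseline BMI, disease duration and baseline HbA1c with no significance screening. Report the active v control odds ratio with 95% CI at month 12; this only clarifies the adjusted output already requested. Describe the analysis as supportive, since model form and missing-data assumptions still differ from LOCF.
- **Quantitative endpoints.** Keep the planned adjusted model as the reported analysis, with robust or bootstrap CIs, or with the log of measured values and covariates retained. Use Mann-Whitney only as a supplementary check, which respects the non-parametric option in Protocol Section 13.

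The cost is SAP wording only, with no new data. The five-covariate GEE of the 5% endpoint could be fitted in 98-100% of simulated datasets, assuming four shared visits and 20-30% control responders; lower control response was not tested. Month-12 rejection at 50% v 20% was 70-82% with all five, against 73-83% with joint screening.
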